6.2. Preparation/Handling/Storage/Accountability

Preparation/Handling/Storage

Apalutamide must be stored at controlled temperatures ranging from 15°C to 30°C.

Refer to the ERLEADA USPI for additional guidance on apalutamide and ADT preparation, handling, and storage.

Accountability

The investigator is responsible for ensuring that all study intervention received at the site is inventoried and accounted for throughout the study. The study intervention administered to the participant must be documented on the intervention accountability form. All study intervention will be stored and disposed of according to the sponsor's instructions. Study-site personnel must not combine contents of the study intervention containers.

Study intervention must be handled in strict accordance with the protocol and the container label, and must be stored at the study site in a limited-access area or in a locked cabinet under appropriate environmental conditions. Unused study intervention, and study intervention returned by the participant, must be available for verification by the sponsor's study site monitor during on-site monitoring visits. The return to the sponsor of unused study intervention, or used returned study intervention for destruction, will be documented on the intervention return form. When the study site is an authorized destruction unit and study intervention supplies are destroyed on-site, this must also be documented on the intervention form.

Study intervention should be dispensed under the supervision of the investigator or a qualified member of the study-site personnel, or by a hospital/clinic pharmacist. Study intervention will be supplied only to participants participating in the study. Returned study intervention must not be dispensed again, even to the same participant. Study intervention may not be relabeled or reassigned for use by other participants. The investigator agrees neither to dispense the study intervention from, nor store it at, any site other than the study sites agreed upon with the sponsor. Further guidance and information for the final disposition of unused study interventions are provided in the Study Site Investigational Product and Procedures Manual.

6.3. Measures to Minimize Bias: Randomization and Blinding (Not Applicable)

6.4. Study Intervention Compliance

Study-site personnel will maintain a log of all study intervention dispensed. Study intervention supplies for each participant will be inventoried and accounted for.

6.5. Dose Modification

Any dose adjustment should be overseen by medically qualified study-site personnel (principal or subinvestigator unless an immediate safety risk appears to be present).

In case a dose modification is necessary, the study intervention will be administered per Section 10.9, Appendix 9, Recommendations for Management of Drug-related Rash.

6.6. Continued Access to Study Intervention After the End of the Study (Not Applicable)

6.7. Treatment of Overdose

For this study, any dose of apalutamide greater than 240 mg within a 24-hour time period will be considered an overdose. The sponsor does not recommend specific intervention for an overdose. There is no specific antidote and treatment should consist of general supportive measures.

In the event of an overdose, the investigator or treating physician should:

- Contact the Medical Monitor immediately.
- Closely monitor the participant for adverse event (AE)/serious adverse event (SAE).
- Document the quantity of the excess dose as well as the duration of the overdosing in the eCRF.
- Decisions regarding dose interruptions or modifications will be made by the investigator in consultation with the Medical Monitor based on the clinical evaluation of the participant.

6.8. Concomitant Therapy

Concomitant therapies must be recorded throughout the study from the time of first dose of study intervention to the last study visit. Concomitant therapies should also be recorded beyond 30 days after last study visit only in conjunction with new or worsening AEs and SAEs that meet the criteria outlined in Section 8.3.1, Time Period and Frequency for Collecting Adverse Event and Serious Adverse Event Information.

All therapies (prescription or over-the-counter medications, including vaccines, vitamins, herbal supplements; non-pharmacologic therapies such as electrical stimulation, acupuncture, special diets, exercise regimens, or other specific categories of interest) different from the study intervention must be recorded in the eCRF. Recorded information will include a description of the type of therapy, duration of use, dosing regimen, route of administration, and indication.

Modification of an effective preexisting therapy should not be made for the explicit purpose of entering a participant into the study.

Prohibited concomitant therapies, outlined in Section 10.6 Appendix 6, include treatment with any AR blocker or CYP17 inhibitor for the treatment of prostate cancer. Sipuleucel-T, pembrolizumab, radium-223, strontium-89, samarium-153, saw palmetto and any agent under investigation and not currently approved by the FDA for any indication are also prohibited. Concomitant therapy restrictions are outlined in Section 10.7, Appendix 7, Restricted Concomitant Medications.

The sponsor must be notified in advance (or as soon as possible thereafter) of any instances in which prohibited therapies are administered.

7. DISCONTINUATION OF STUDY INTERVENTION AND PARTICIPANT DISCONTINUATION/WITHDRAWAL

7.1. Discontinuation of Study Intervention

A participant's study intervention must be discontinued if:

- The participant withdraws consent to receive study intervention
- The investigator believes that for safety reasons or tolerability reasons (eg, AE) it is in the best interest of the participant to discontinue study intervention
- Noncompliance with study intervention administration
- Participants experiencing treatment-related seizure of any grade will have apalutamide permanently discontinued

If a participant discontinues study intervention for any reason before the end of the study, then the last scheduled study assessments should be obtained and scheduled assessments off study intervention should be continued. If a participant misses doses for >28 days, consult the sponsor regarding continuation in the study. If a participant discontinues study intervention due to disease progression, the subsequent treatment including radiation will be captured in the eCRF, if known. Additional participants will not be entered to ensure the protocol-specified number of participants complete the study.

7.1.1. Rechallenge

If a participant experiences a \geq Grade 3 toxicity or an intolerable side effect, hold dosing until symptoms improve to \leq Grade 1 or original grade, then resume at the same dose or a reduced dose, if warranted per Section 10.9, Appendix 9, Recommendations for Management of Drug Related Rash.

7.2. Participant Discontinuation/Withdrawal From the Study

A participant will be withdrawn from the study for any of the following reasons:

- Lost to follow-up
- Withdrawal of consent

- Investigator's discretion
- Seizure
- Death

When a participant withdraws before study completion, the reason for withdrawal is to be documented in the eCRF and in the source document. If the reason for withdrawal from the study is withdrawal of consent, then no additional assessments are allowed.

Withdrawal of Consent

A participant declining to return for scheduled visits does not necessarily constitute withdrawal of consent. Alternate follow-up mechanisms that the participant agreed to when signing the consent form apply (eg, consult with family members, contacting the participant's other physicians, medical records, database searches, use of locator agencies at study completion) as local regulations permit.

Prior to a participant withdrawing consent for follow-up, the investigator should offer the participant an opportunity for one of the alternative reduced follow-up mechanisms described below. Withdrawal of consent should be an infrequent occurrence in clinical studies, therefore, prior to the start of the study, the sponsor and the investigator should discuss and reach a clear understanding of what constitutes withdrawal of consent in the context of the available reduced follow-up mechanisms listed.

7.2.1. Withdrawal From the Use of Research Samples

A participant who withdraws from the study will have the following options regarding the research samples:

- The collected samples will be retained and used in accordance with the participant's original informed consent.
- The participant may withdraw consent for research samples, in which case the samples will be destroyed, and no further testing will take place. To initiate the sample destruction process, the investigator must notify the sponsor study site contact of withdrawal of consent for the research samples and to request sample destruction. The sponsor study site contact will, in turn, contact the biomarker representative to execute sample destruction. If requested, the investigator will receive written confirmation from the sponsor that the sample has been destroyed.

Withdrawal From the Use of Samples in Future Research

The participant may withdraw consent for use of samples for research (refer to Long-term Retention of Samples for Additional Future Research in Section 10.3, Appendix 3, Regulatory, Ethical, and Study Oversight Considerations). In such a case, samples will be destroyed after they are no longer needed for the clinical study. Details of the sample retention for research are presented in the main informed consent form (ICF).

7.3. Lost to Follow-up

To reduce the chances of a participant being deemed lost to follow-up, prior to study entry, attempts should be made to obtain contact information from each participant, eg, home, work, and mobile telephone numbers and email addresses for both the participant as well as appropriate family members.

Participants will be considered lost to follow-up if they repeatedly fail to return for scheduled visits and is unable to be contacted by the study site. A participant cannot be deemed lost to follow-up until all reasonable efforts made by the study-site personnel to contact the participant are deemed futile. The following actions must be taken if a participant fails to return to the study site for a required study visit:

- The study-site personnel must attempt to contact the participant to reschedule the missed visit as soon as possible, to counsel the participant on the importance of maintaining the assigned visit schedule, to ascertain whether the participant wishes to or should continue in the study.
- Before a participant is deemed lost to follow up, the investigator or designee must make every reasonable effort to regain contact with the participant (where possible, 3 telephone calls, e-mails, fax, and, if necessary, a certified letter to the participant's last known mailing address, or local equivalent methods). These contact attempts should be documented in the participant's medical records.
- Should the participant continue to be unreachable, they will be considered to have withdrawn from the study.

Should a study site close, eg, for operational, financial, or other reasons, and the investigator cannot reach the participant to inform them, their contact information will be transferred to another study site.

7.4. National Disaster/Extra Ordinary Circumstances

If appropriate, site visits may be replaced with telephone visits during a national disaster or extra ordinary circumstances, with site visits resuming as soon as possible thereafter. Telephone visits will be recorded in the source documentation and eCRF. If a visit included blood collection, the collection and testing may be done at a facility closer to the participant. A copy of the laboratory report, along with the reference ranges must be obtained for the source documentation and provided with the eCRF. Study intervention may be dispensed by alternative methods (for example shipped to participants). Refer to Section 10.12, Appendix 12, Guidance on Study Conduct during the COVID-19 Pandemic, for details related to the COVID pandemic that may also be applied to other national disasters or extra ordinary circumstances.

8. STUDY ASSESSMENTS AND PROCEDURES

Overview

The Schedule of Activities summarizes the frequency and timing of efficacy, biomarker, safety measurements applicable to this study.

The PSA assessments should be conducted/completed before any tests, procedures, or other consultations to prevent influencing participant perceptions.

Blood collections should be kept as close to the specified time as possible. Other measurements may be done earlier than specified timepoints if needed. Actual dates and times of assessments will be recorded in the source documentation and eCRF.

The total blood volume for the main study is approximately 55 mL.

Repeat or unscheduled samples may be taken for technical issues with the samples.

Sample Collection and Handling

Refer to Section 1.3, Schedule of Activities for the timing and frequency of all sample collections.

Study-Specific Materials

The investigator will be provided with the following information:

- IB and ERLEADA USPI for apalutamide and USPI for ADT
- Pharmacy Manual/Study Site Investigational Product and Procedures Manual
- National Cancer Institute Common- Terminology Criteria for Adverse Events (NCI-CTCAE) Version 5.0
- Response Evaluation Criteria in Solid Tumors (RECIST) guidelines Version 1.1
- Electronic data capture (eDC) Manual
- eSource Manual
- ICF template

8.1. Efficacy Assessments

Efficacy assessments include serum PSA and testosterone and will be assessed prior to first dose of study intervention and throughout the study per the SoA. A PSA level >0.2 ng/mL (confirmed within 3-4 weeks) will be considered an indicator of BCR.

8.2. Safety Assessments

Participants will be monitored for safety from the beginning of the treatment and at each study visit. Events related to and associated with the recovery from the pre-planned RP will not be collected.

Details regarding the Steering Committee are provided in Committees Structure in Section 10.3 Appendix 3, Regulatory, Ethical, and Study Oversight Considerations.

Adverse events will be reported and followed by the investigator as specified in Section 8.3, Adverse Events and Serious Adverse Events and Section 10.4, Appendix 4, Adverse Events,

Serious Adverse Events, Product Quality Complaints, and Other Safety Reporting: Definitions and Procedures for Recording, Evaluating, Follow-up, and Reporting.

Any clinically relevant changes occurring during the study must be recorded on the AE section of the eCRF.

Any clinically significant abnormalities persisting at the end of the study/early withdrawal will be followed by the investigator until resolution or until a clinically stable condition is reached.

The study will include the following evaluations of safety and tolerability according to the time points provided in the SoA.

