- a Beginning with Visits 2 through 8, a window of ±7 calendar days for scheduling will be allowed.
- b Beginning with Visit 9 and for all follow-up visits, a window of ±14 calendar days for scheduling will be allowed.
- c Must be signed before first study-related activity.
- d Provide 3-month supply of apalutamide during Visits 4, 5, and 6.
- e ADT first administration will be at baseline and subsequently administered per USPI for total duration 12 months, 3-month depot is the preferred administration. NOTE: If 3-month DEPOT is used, the last dose will be administered at Month 10. If 3-month DEPOT is not used, follow USPI.

- Clinical Protocol 56021927PCR2041 Amendment 2
- f A PSA level >0.2 ng/mL will be an indicator of BCR and will be confirmed within 3 to 4 weeks regardless of study visit and timing. Depending on timing, this may be captured as an unscheduled visit.
- g Focused examinations are generally limited to the body systems or regions based on participant's self-assessment and AE reporting. Any new complaints, symptoms reported by participants or adverse events noted by providers should guide the need and extent of physical examination.
- h ECG assessment at screening if not available from preoperative information.
- i Collected at baseline, 12 months or end of treatment, and at 24 months or progression (whichever comes first).
- j Tissue sample to be collected and sent to sponsor's laboratory partner along with a copy of the full histopathology report of the specimen. Biopsy tissue is preferred. See Section 8.6 for further details.
- k Collection of concomitant therapies does not begin until time of first dose of apalutamide.
- ^L Collection of AEs does not begin until time of first dose of apalutamide.

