6. STUDY INTERVENTION

6.1. Study Intervention Administered

The study intervention apalutamide, 240 mg (four 60 mg tablets, slightly yellowish to greyish green oblong film-coated tablets, debossed with "AR 60" on one side), will be provided as tablets for oral administration. The window for initiation of study intervention must occur between Day 29 and Day 90 post-RP. Participants will be instructed to take their assigned dose of the study intervention orally **once daily** for 12 cycles per ERLEADA USPI. A treatment cycle is defined as 28 days. Apalutamide can be taken with or without food. If a participant experiences a \geq Grade 3 toxicity or an intolerable side effect, hold dosing until symptoms improve to \leq Grade 1 or original grade, then resume at the same dose or a reduced dose (180 mg or 120 mg), if warranted. If a participant remains off apalutamide for \geq 4 weeks, the participant may be withdrawn from the study, after discussing with the sponsor. Participants experiencing treatment related seizure of any grade will have apalutamide permanently discontinued.

Description of Interventions

Study intervention administration must be captured in the source documents and the electronic case report form (eCRF). Study-site personnel will instruct participants on how to store study intervention for at-home use as indicated for this protocol.

Apalutamide will be manufactured and provided under the responsibility of the sponsor. Refer to the IB for a list of excipients and the ERLEADA USPI.

Investigator's choice of a Food and Drug Administration (FDA)-approved and commercially available ADT, not provided by the sponsor, will be administered per the USPI for 12 months in total duration, during the treatment phase. Three-month depot is the preferred administration. For further information on ADT refer to the USPI.

For a definition of study intervention overdose, refer to Section 6.7, Treatment of Overdose.

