8.3. Adverse Events and Serious Adverse Events

Timely, accurate, and complete reporting and analysis of safety information from clinical studies are crucial for the protection of participants, investigators, and the sponsor, and are mandated by regulatory agencies worldwide. The sponsor has established Standard Operating Procedures in conformity with regulatory requirements worldwide to ensure appropriate reporting of safety

information; all clinical studies conducted by the sponsor or its affiliates will be conducted in accordance with those procedures.

Adverse events will be reported by the participant (or, when appropriate, by a caregiver, surrogate, or the participant's legally acceptable representative) for the duration of the study.

For further details on AEs and SAEs (Definitions and Classifications; Attribution Definitions; Severity Criteria; Special Reporting Situations; Procedures) as well as product quality complaints, refer to Section 10.4, Appendix 4, Adverse Events, Serious Adverse Events, Product Quality Complaints, and Other Safety Reporting: Definitions and Procedures for Recording, Evaluating, Follow-up, and Reporting.

8.3.1. Time Period and Frequency for Collecting Adverse Event and Serious Adverse Event Information

All Adverse Events

Monitoring of AEs will be performed at 1, 2, 3, 4, 7, 10, 13, 14 months, at each follow-up visit, and during phone calls with the participants. All AEs and special reporting situations, whether serious or non-serious, will be reported from the time after the participant receives the first dose of apalutamide until completion of the participant's last study-related procedure, which may include contact for follow-up of safety. Serious adverse events, including those spontaneously reported to the investigator within 30 days after the last dose of study intervention, must be reported using the SAE Form. The sponsor will evaluate any safety information that is spontaneously reported by an investigator beyond the time frame specified in the protocol.

Serious Adverse Events

All SAEs occurring during the study must be reported to the appropriate sponsor contact person by study-site personnel within 24 hours of their knowledge of the event.

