8.3.6. Cardiovascular and Death Events

Ischemic cardiovascular events, including events leading to death, occurred in patients receiving apalutamide. Monitor for signs and symptoms of ischemic heart disease. Optimize management of cardiovascular risk factors, such as hypertension, diabetes, or dyslipidemia. Consider discontinuation of apalutamide for Grade 3 and 4 events.

8.3.7. Disease-Related Events and Disease-Related Outcomes not Qualifying as Adverse Events or Serious Adverse Events

All events that meet the definition of an SAE will be reported as SAEs, regardless of whether they are protocol-specific assessments.

Disease progression should not be recorded as an AE or SAE term; instead, signs and symptoms of clinical sequelae resulting from disease progression/lack of efficacy will be reported if they fulfil the SAE definition (refer to Adverse Event Definitions and Classifications in Section 10.4, Appendix 4, Adverse Events, Serious Adverse Events, Product Quality Complaints, and Other Safety Reporting: Definitions and Procedures for Recording, Evaluating, Follow-up, and Reporting). Expected progression of disease should not be considered an AE (or SAE). However, if determined by the investigator to be more likely related to the study intervention than the underlying disease, the clinical signs or symptoms of progression and the possibility that the study

intervention is enhancing disease progression, should be reported per the usual reporting requirements.

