10.4.5. Procedures

All Adverse Events

All AEs, regardless of seriousness, severity, or presumed relationship to study intervention, must be recorded using medical terminology in the source document and the eCRF. Whenever possible, diagnoses should be given when signs and symptoms are due to a common etiology (eg, cough, runny nose, sneezing, sore throat, and head congestion should be reported as "upper respiratory infection"). Investigators must record in the eCRF their opinion concerning the relationship of the AE to study therapy. All measures required for AE management must be recorded in the source document and reported according to sponsor instructions.

For all studies with an outpatient phase, including open-label studies, the participant must be provided with a "wallet (study) card" and instructed to carry this card with them for the duration of the study indicating the following:

- Study number
- Statement, in the local language(s), that the participant is participating in a clinical study
- Investigator's name and 24-hour contact telephone number
- Local sponsor's name and 24-hour contact telephone number (for medical personnel only)
- Site number
- Participant number

Serious Adverse Events

All SAEs that have not resolved by the end of the study, or that have not resolved upon discontinuation of the participant's participation in the study, must be followed until any of the following occurs:

- The event resolves
- The event stabilizes
- The event returns to baseline, if a baseline value/status is available
- The event can be attributed to agents other than the study intervention or to factors unrelated to study conduct
- It becomes unlikely that any additional information can be obtained (participant or health care practitioner refusal to provide additional information, lost to follow-up after demonstration of due diligence with follow-up efforts)

Suspected transmission of an infectious agent by a medicinal product will be reported as an SAE. Any event requiring hospitalization (or prolongation of hospitalization) that occurs during the course of a participant's participation in a study must be reported as an SAE, except hospitalizations for the following:

- Hospitalizations not intended to treat an acute illness or AE (eg, social reasons such as pending placement in long-term care facility)

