- Most frequent treatment-related Grades 3 and 4 AEs (reported in \geq 5% of subjects in either the investigational or control group)
- Treatment-related Grades 3 or 4 AEs by decreasing frequency of preferred term
- All AEs that led to death by SOC and preferred term
- All AEs that led to study drug discontinuation by SOC and preferred term. Study drug discontinuation will be determined from the End of Treatment CRF (where reason for termination is "Adverse Event") and the specific AE will be determined from the AE eCRF page (where action taken is "Withdrawn from Study")
- All AEs that led to study drug discontinuation by SOC, preferred term, and toxicity grade
- All AEs that lead to study drug dose modification by SOC and preferred term
- All SAEs by SOC and preferred term
- All SAEs by SOC, preferred term, and toxicity grade
- Deaths by time period (Treatment Phase, Follow-up Phase) and cause of death

Subject listings of all Grades 3 or 4 AEs, all SAEs, AEs that led to study drug discontinuation, dose modification, and all deaths will be provided as well. If there are any AEs attributed to RP (e.g. lymphocele, intraoperative bleeding, postoperative bleeding, urinary incontinence), listings of all AEs (or relevant tables if there is a large of proportion of these subjects) will also be provided.

Narratives will be written for the following subjects in the final clinical study report:

- Subjects who die due to treatment-related adverse events ≤ 30 days after the last dose of study drug
- Subjects who discontinue study drug due to adverse events
- Subjects who have a treatment-related serious adverse event
- Subjects who experience a seizure

Subjects who experience other Grade 3 or higher treatment-emergent adverse events of special interest.

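### The rule against collecting prostatectomy-recovery events has no onset limit or SAE exception, so it can only affect on-treatment events and conflicts with the protocol's all-AE and all-SAE rules and with SAP 5.6.2

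*Protocol*

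**What the plan says.** Protocol 8.2 states, directly after saying that safety is monitored from the beginning of treatment: "Events related to and associated with the recovery from the pre-planned RP will not be collected". The synopsis (1.1) and the sub-study's safety section (10.13.10.2) repeat the sentence unchanged. None of the three gives a cut-off date or an exception for serious events.

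The other rules on the same subject are:

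- **Timing of dosing (Protocol 6.1):** "The window for initiation of study intervention must occur between Day 29 and Day 90 post-RP".
- **Start of collection (Protocol 1.3, footnote to the schedule):** "Collection of AEs does not begin until time of first dose of apalutamide". In the sub-study, collection starts at the first dose of relugolix (10.13.3, footnote k).
- **Scope of AE reporting (Protocol 8.3.1):** "All AEs and special reporting situations, whether serious or non-serious, will be reported from the time after the participant receives the first dose of apalutamide".
- **Scope of SAE reporting (Protocol 8.3.1):** "All SAEs occurring during the study must be reported to the appropriate sponsor contact person by study-site personnel within 24 hours" of learning of the event.
- **Serious events (Protocol 8.3.7):** "All events that meet the definition of an SAE will be reported as SAEs".
- **Attribution (Protocol 10.4.5):** "All AEs, regardless of seriousness, severity, or presumed relationship to study intervention, must be recorded".
- **Analysis (SAP 5.6.2):** listings, or tables if many participants are affected, are planned under this condition: "If there are any AEs attributed to RP (e.g. lymphocele, intraoperative bleeding, postoperative bleeding, urinary incontinence" and similar).

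**The concern.** Read literally, 8.2 lets a site leave out an on-treatment event because someone judges that it belongs to surgical recovery. That judgment would be made before any record exists, so it could be neither audited nor reversed in the analysis. The other rules tell the same site to record the event and let the analysis deal with attribution.

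The study is open-label with no control arm, so there is no concurrent rate against which under-recording would show. Attribution to surgery is easiest in the first weeks of dosing, which may begin about four weeks after the operation. The events most exposed are late surgical complications such as an infected lymphocele, postoperative bleeding and urinary events. Thromboembolism is possible too; exclusion criterion 9.2 already names it as a risk to screen for.

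At stake are the completeness of early treatment-emergent AE and SAE rates and consistency across about 30 practices. The sub-study is affected as well, since adverse events through Day 28 are its secondary endpoint. The main study's primary and secondary efficacy endpoints are not touched.

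**Working it through.** The plan states no figure that this point depends on. The check is mainly a comparison of text, with some arithmetic on scale.

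**1. What can the sentence still exclude?**

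- Events that start and end before first dose are already outside collection (1.3 footnote, 8.3.1, 10.4.1).
- Symptoms present at first dose and unchanged since are neither new nor aggravated from baseline, so they fall outside the AE elaboration in 10.4.1.
- What remains is events that begin or worsen after first dose. Only there can the sentence change what is recorded.

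**2. Does treatment time overlap with surgical recovery?**

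A cycle is 28 days. With first dose on postoperative Day 29, Cycle 1 covers Day 29 to 29 + 27 = Day 56. With first dose on Day 90, it covers Day 90 to 90 + 27 = Day 117. Late surgical complications can fall in these windows.

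**3. Side by side, for an infected lymphocele with admission two weeks after first dose**

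| Place | Instruction |
|---|---|
| Protocol 8.2 (also 1.1, 10.13.10.2) | Not collected, if judged part of RP recovery |
| Protocol 8.2, later in the section | Clinically relevant changes go on the AE section of the eCRF |
| Protocol 8.3.1 | Reported as an AE; as an SAE within 24 hours |
| Protocol 8.3.7 | Reported as an SAE |
| Protocol 10.4.5 | Recorded whatever the presumed relationship |
| SAP 5.6.2 | Listed as RP-attributed (lymphocele is named) |

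The hospitalisation exceptions in 10.4.5 do not resolve this. They cover surgery planned before study entry, and an AE that prolongs such a stay is itself to be reported as a new SAE. A later complication is not exempted.

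**4. Scale**

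- Main study: one unrecorded participant-event is 1/94 = 1.1 percentage points. Sub-study: 1/12 = 8.3 points.
- Illustration with assumed counts of one event type and exact (Clopper-Pearson) one-sided 95% upper limits:

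| Events that occurred (assumed) | True proportion | Upper limit | Reported if none recorded | Upper limit then shown |
|---|---|---|---|---|
| 2 of 94 | 2.1% | 6.5% | 0% | 3.1% |
| 4 of 94 | 4.3% | 9.5% | 0% | 3.1% |

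For zero events the limit is 1 − 0.05^(1/94) = 3.1%. The counts of 2 and 4 are not in the documents. They show only how sensitive the summaries are at this sample size.

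**The case against.** The strongest reply is that a site following the operative procedures would report these events anyway. Section 8.2 itself refers AE reporting to 8.3 and 10.4, and nothing gives its one sentence precedence over them. A reader might infer that serious early events will be lost, or that attribution alone decides whether an event is recorded. The documents do not support either inference. They contain conflicting instructions, so the most that follows is that events could go unrecorded.

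Other points limit the concern:

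- **Recovery is required for entry.** Inclusion criterion 4.1 asks for recovery from RP and no peri-operative worsening of cardiac risk. The note closing section 5.2 excludes anyone who ceases to qualify before first dose. This should make recovery events on treatment few, but not zero.
- **Intent.** The rationale in the Amendment 1 history links avoiding RP-associated AEs to starting collection at dosing. That suggests no separate on-treatment filter was meant. It does not change the current wording, which goes beyond that aim.
- **The choice of example.** A new pulmonary embolism during treatment is a new-onset event and not plainly part of recovery. The lymphocele, which the SAP names, is the fairer case.
- **The SAP listing is conditional.** It foresees that there may be no such AEs, and its mention of intraoperative bleeding looks generic. Still, it shows that RP-attributed AEs were expected in the database, contrary to 8.2.
- **Oversight.** No independent data monitoring committee is planned (SAP 5.8.1), but the Steering Committee's remit includes participants' continued safety (Protocol 10.3.6). No committee can review events that were never recorded.

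These points reduce the likely size. They leave the conflict in place.

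**Conclusion.** This is an internal inconsistency in the current text and should be reconciled. Confidence in the conflict is high: the sentence appears three times without limit, it can act only on events that begin or worsen on treatment, and sections 8.3.1, 8.3.7 and 10.4.5 and SAP 5.6.2 contain no matching exception.

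Confidence in the consequence is lower. Early treatment-emergent AE and SAE rates could be understated, and sites could differ in what they record. The size is unknown, because the documents give neither an expected rate of late RP complications nor any indication of how sites would resolve the conflict. It is probably limited by the recovery criterion. The conclusion assumes only that some events starting after first dose could reasonably be judged part of surgical recovery, as SAP 5.6.2 itself anticipates.

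**What to change.** - **Protocol 1.1, 8.2 and 10.13.10.2:** limit the sentence to events with onset before the first dose of apalutamide (of relugolix in the sub-study), or delete it. Deletion loses nothing, since the start-of-collection rule already has that effect.
- **Same places:** state that from first dose every AE and SAE is recorded under 8.3.1 and 10.4.5, including worsening of an earlier recovery event, which 10.4.1 already treats as an AE.
- **eCRF:** add a yes/no flag for attribution to RP.
- **SAP 5.6.2:** produce the planned RP listing from the flag, and show AE summaries with and without flagged events. Surgical events can then be separated openly at analysis. Bare reconciliation does not strictly need the flag, but it gives the listing a defined source.

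The cost is three sentences, one eCRF field and one extra table. The downside is some additional low-grade postoperative AE entries and slightly higher reported AE rates, which the split summary would explain.
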